1.3 SCHEDULE OF ACTIVITIES (SOA)

	Clinic Visits					Follow-Up				
			Study	/ Trea	tment Visits		Clinic Check	Early Stop		
Procedures (Time to Complete)	Initial Evaluation*	#1*	# 2 - # 4	# 5	#6-#11	# 12 or Week 8, or when Return To Sport Criteria Met		Visit	30 –Day By Phone	90-Day By Survey
Standard PT Treatment	x									
Standard PT Treatment		x					X			
Inclusion/ Exclusion Criteria		х								
Informed Consent		х								
Randomization		х								
FACES Pain Scale		x	x	х	x	Х	х	х		
Brief Physical Exam of the Targeted Knee		х	x	x	х	х	х	x		
Medication Review		x	х	х	х	х	х	х	х	х
Adverse Events Evaluation		x	х	х	х	х	х	х	х	х
Lower Extremity Functional Scale (LEFS)		x		x		х		x	х	
Return to Sport Criteria (RTS) Checklist		x	x	x	х	х	х			
Godin Leisure-Time Exercise Questionnaire		х							х	x
Compliance Check to Home Exercise Program, Patch Wear Time, Ice Application, Bracing, and Activity Restrictions		x	x	x	х	Х	x	x		
Iontophoresis Treatment (Groups A and B only)		X-				Х				
Complete Case Report Forms		х	х	х	х	х	х	х	х	х

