4 STUDY DESIGN

4.1 OVERALL DESIGN

The primary study hypothesis is that the time to achieve RTS criteria for pediatric patients with apophysitis of the knee who receive iontophoresis with DSP treatment and PT will be different than those who receive placebo or PT alone. The secondary study hypotheses are: that the patient reported outcomes for pediatric patients with apophysitis of the knee who receive iontophoresis with DSP treatment and PT will be different than those who receive placebo or PT alone; and the frequency and intensity of adverse events among pediatric patients with apophysitis of the knee who receive placebo or PT alone.

This is a Phase II trial. It is a three-arm, randomized, double-blind, placebo-controlled comparison study looking at the functional and patient reported outcomes of iontophoresis (with DSP or placebo) in conjunction with PT versus PT alone to treat pediatric patients diagnosed with apophysitis of the knee.

The study is double-blinded and placebo-controlled to minimize bias. There will be three (3) study groups

- Iontophoresis using DSP (study drug) + PT
- Iontophoresis using placebo + PT
- o PT alone

Participants in all three groups will receive the standard PT protocol for apophysitis of the knee. This will involve up to 20 visits. Participants randomized to the iontophoresis groups will receive up to 12 iontophoresis treatments over a maximum of eight (8) weeks. All participants will receive a phone follow-up call 30 days after they meet RTS criteria as well as an electronic survey follow-up 90 days after they meet RTS criteria.

This study will only be conducted through the Children's Hospital of the King's Daughters Sports Medicine PT Department with study-related activities occurring at six of CHKD's Hampton Roads PT clinics. All study-related activities will be completed by Physical Therapists and Physical Therapist Assistants (Treating Therapists) trained on the protocol and CITI trained.

Concomitant therapies, age, gender, and race will be conducted to analyze the possible effects of these covariates on length of time to RTS

Stratifications of age, gender, and race will be conducted to analyze the possible effect of these covariates on length of time to RTS as well as on patient reported outcomes LEFS, Godin Leisure-Time Activity, and FACES Pain Scale and on safety outcomes.

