8 STUDY ASSESSMENTS AND PROCEDURES

8.1 EFFICACY ASSESSMENTS

As Standard of Care:

- All patients who are referred to the participating PT clinics with a diagnosis of apophysitis of the knee and a prescription for PT with iontophoresis will receive a PT Initial Evaluation (IE).
 Per department policy, the PT IE must take place within 90 days of referral date as indicated on the script.
 - The IE includes: review of demographics, medical history, medication regime, strength and balance tests, pain assessment, review of home exercise program, icing instructions, activity restrictions, and bracing and NSAID instructions as recommended by their referring physician.
- After the IE, and as part of standard of care, all participants, regardless of group assignment, will receive a standardized PT treatment progression provided by qualified therapists.
 - As standard of care, PT progression visits may include up to 19 visits
- Clinic Check Visit Two (2) to three (3) business days after a participant is cleared for RTS, or has received treatment for eight (8) weeks, whichever is sooner, the participant will return to the

clinic for the Treating Therapist to confirm the participant remains pain free and able to meet the RTS criteria.

• Physical therapy progression visits to further fine tune mechanics, strength, and stretch may occur after this visit as part of their standard of care.

Study-related:

Study-related procedures will begin on the first PT Treatment Day, which may be the same day as the IE or at the next PT visit, but never before the Consent is signed. If subjects meet inclusion/exclusion criteria and the potential participant consents to participate at the Initial PT Evaluation Visit, the IE and Enrollment/Randomization Study Treatment Visit 1 visits may be combined.

The following procedures/evaluations will be obtained by the Treating Therapists:

- Lower Extremity Function Scale (LEFS) (see Appendix 12.1) a patient reported paper-based questionnaire that asks the patient to choose the level of difficulty of completing 20 different activities. Assessed at Study Treatment Visits 1, 5, 12/RTS Criteria Met Visit, and 30-day Follow Up. Note: the LEFS will be administered over the phone at the 30-day Follow-Up Visit.

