9.2 SAMPLE SIZE DETERMINATION

To assess the primary variable of interest, a power analysis indicated that a total sample of 126 participants would be required to detect medium effects (f = 0.28) with 80% power and $\alpha = 0.05$ using Generalized Linear Model (GLM).

The required sample size to test secondary hypotheses was calculated as 87 and 108 participants for patient reported outcomes and safety, respectively. Therefore, a total sample of 126 participants provides sufficient power for testing secondary hypotheses.

Given an estimated 15% non-compliance rate, the sample size will be increased by 15%, for a total sample size of 147 participants (49 per group).

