9.4.3 ANALYSIS OF THE SECONDARY ENDPOINT(S)

For each secondary endpoint:

A Generalized Estimation Equation (GEE) Model, including baseline records, will be used to check for changes in LEFS, FACES pain scale, and Godin Leisure-Time Exercise between treatment groups over time. Results for LEFS and Godin Leisure-Time Exercise will be presented as mean with 95% confidence interval, and results for FACES pain scale will be reported as odds ratio and 95% confidence interval.

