12 APPENDICES

12.1 LOWER EXTREMITY FUNCTIONAL SCALE (LEFS)

Lower Extremity Functional Index

We are interested in knowing whether you are having any difficulty at all with the activities listed below because of your lower limb problem for which you are currently seeking attention. Please provide an answer for each activity.

Today, do you or would you have any difficulty at all with:

Activities	Extreme Difficulty or unable to perform activity	Quite a bit of difficulty	Moderate difficulty	A little bit of difficulty	No difficulty
a. Any of your usual work, housework or school activities.	0	1	2	3	4
b. Your usual hobbies, recreational or sporting activities	0	1	2	3	4
c. Getting into or out of the bath.	0	1	2	3	4
d. Walking between rooms.	0	1	2	3	4
e. Putting on your shoes or socks.	0	1	2	3	4
f. Squatting.	0	1	2	3	4
g. Lifting an object, like a bag of groceries from the floor.	0	1	2	3	4
h. Performing light activities around your home.	0	1	2	3	4
i. Performing heavy activities around your home.	0	1	2	3	4
j. Getting into or out of a car.	0	1	2	3	4
k. Walking 2 blocks.	0	1	2	3	4
I. Walking a mile.	0	1	2	3	4
m. Going up or down 10 stairs (about 1 flight of stairs).	0	1	2	3	4
n. Standing for 1 hour.	0	1	2	3	4
o. Sitting for 1 hour.	0	1	2	3	4
p. Running on even ground.	0	1	2	3	4
q. Running on uneven ground.	0	1	2	3	4
r. Making sharp turns while running fast.	0	1	2	3	4
s. Hopping.	0	1	2	3	4
t. Rolling over in bed.	0	1	2	3	4
COLUMN TOTALS					

(Circle one number on each line)

Score variation ± 6 LEFTS points MDC & MCID = 9 LEFS points

Score ____/80

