12.2 WONG BAKER FACES PAIN SCALE

12.3 RETURN TO SPORT CHECKLIST

Phase 1 - Nonimpact

. Pain-free ADL's

□Squats x 10 pain-free with proper mechanics (all of the following must be met:)

□No anterior tibial translation

□ Heels stay in contact with the ground

□Neutral/slight external rotation foot placement

 \Box Knee stays in line with 2nd toe

□Trunk upright

□No trunk shift

NOTE: Must meet both Phase 1 criteria before progressing to Phase 2 criteria. Phase 2 criteria must be assessed/completed in the order listed below.

Phase 2 - Impact

Broad jumps x10 pain-free with proper mechanics (all of the following must be met:)

□Knee in line with 2nd toe on take-off and landing

□No anterior tibial translation on landing

□Even footing on take-off and landing

□Soft landing

□ Pain free

□Single leg triple hop for distance (all of the following must be met:)

□ Met all above criteria for broad jumping

 \Box No loss of balance

 \Box No extra hop on landing

□No touching down of either the contralateral lower extremity or the upper extremity

□Stick and hold final landing for at least 3 seconds

□Affected lower extremity within 85% of the unaffected lower extremity

□ Pain-free

□ Modified T-test

□ Met all above criteria for single leg triple hop for distance

 \Box 100% effort

 \Box Pain-free

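### LEFS after Visit 5 is dated by return to sport; 9.4.3 should adjust for baseline LEFS, name the arm pairs and say how children with confirmed return to sport before Visit 5 are handled

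*Combined protocol and SAP*

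**What the plan says.** Section 8.1 sets the LEFS times: "Assessed at Study Treatment Visits 1, 5, 12/RTS Criteria Met Visit, and 30-day Follow Up". In the Schedule of Activities (1.3) the third of these falls under the column "12 or Week 8, or when Return To Sport Criteria Met", and there is also an Early Stop LEFS. The fourth is dated in 4.1: "All participants will receive a phone follow-up call 30 days after they meet RTS criteria". Study Treatment Visits stop at RTS (8.1), but a child who fails the Clinic Check goes back on assigned treatment.

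The RTS checklist and the LEFS cover similar ground. The checklist (12.3) requires pain-free squats, jumps and a "Single leg triple hop for distance". The LEFS (12.1) asks about squatting, hopping and "Making sharp turns while running fast".

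Section 9.4.3 specifies a GEE, with baseline among the records, that "will be used to check for changes in LEFS, FACES pain scale, and Godin Leisure-Time Exercise between treatment groups over time". It names no visit, arm pair, time coding or working correlation. Section 9.2 gives 87 participants for patient-reported outcomes and concludes that "a total sample of 126 participants provides sufficient power for testing secondary hypotheses", without stating a LEFS effect, SD, visit or contrast. The form itself gives "MDC & MCID = 9 LEFS points".

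**The concern.** The trial's main hypothesis concerns time to recovery. If DSP works by speeding recovery, a LEFS taken at RTS compares children in a similar recovered state, however quickly each arrived there. The call 30 days later does the same. Visit 5 is the only scheduled post-baseline LEFS that RTS does not date, and even that visit does not occur for a child whose RTS was confirmed earlier.

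Three consequences follow.

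- A null LEFS result at RTS or 30 days later could be misread as no functional benefit.
- Comparing change from baseline, where adjustment for baseline is available, gives up power at no gain.
- Leaving out the quickest recoverers at Visit 5 removes more good outcomes from the better arm, if there is one, and so understates the difference there.

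**Working it through.** **1. The plan's own figures.** One-way ANOVA, three groups, f = 0.28, two-sided alpha 0.05: noncentrality = N x f² = 126 x 0.0784 = 9.88. Power is 0.8002, and 126 is the smallest N that reaches 80%. The figure of 87 has no stated inputs. A between-group test averaged over three measures with correlation 0.5 has noncentrality N x f² x 3/(1 + 2 x 0.5) = 87 x 0.0784 x 1.5 = 10.23, power 0.810 (0.795 at 84). So 87 fits an averaged contrast. Those inputs are inferred, so this is suggestive only.

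**2. Change versus adjustment.** With equal SD s at both times and correlation r, the variance of a change is 2s²(1 - r) and that of a baseline-adjusted value is s²(1 - r²). The ratio, adjusted to change, is (1 + r)/2: 0.65 at r = 0.3, 0.75 at 0.5, 0.85 at 0.7. If scores bunch near the ceiling at RTS, the change score still carries all the baseline spread, so the loss is larger.

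**3. Simulated size of that loss** (recovery 1.5 times faster on DSP, 42 per arm = 126/3):

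- 32 assumed courses, 400 trials each: averaged contrast 14-58% with change, 39-97% with baseline adjustment. Monte Carlo standard error is at most √(0.25/400) = 2.5 points.
- 96 assumed courses, DSP vs placebo: joint by-visit test, median 31% with change and 47% with baseline adjustment. Inputs: baseline 54, SD 8, ceiling 80, measurement SD 3.6, exponential or linear recovery, RTS in 45% or 65% of controls, visits every 3.5 or 5.1 days.

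**4. Children without a Visit 5 LEFS.** With a median recovery half-time of 28 days and a 1.5-fold speed-up, 11% of DSP and 6-7% of control children reached RTS before Visit 5. The Visit 5 difference was 3.21 points with every child counted and 2.84 with observed values only (loss 0.37). At a 2-fold speed-up the shares were 17% and 6%, and the difference was 5.76 against 4.94 (loss 0.82). Across the 32 courses at 1.5-fold the loss reached about 1.1 points.

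Power in a separate three-arm simulation, 1.5-fold, 42 per arm, all tests baseline-adjusted, every early RTS taken as confirmed. Only the column marked RTS value fills in early-RTS children:

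| Half-time (days) | RTS before Visit 5, DSP / control | Joint | Visit 5 observed | Visit 5 with RTS value | Average |
|---|---|---|---|---|---|
| 8 | 62% / 40% | 18.6% | 18.8% | 33.3% | 22.9% |
| 14 | 32% / 18% | 29.9% | 34.6% | 52.8% | 41.3% |
| 20 | 19% / 10% | 37.1% | 40.8% | 52.1% | 51.8% |
| 28 | 11% / 6% | 46.0% | 44.1% | 49.7% | 59.1% |

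Observed-only Visit 5 is within about 5 points of the joint test. The gain comes from the rule for early RTS: 14.5, 18.2, 11.3 and 5.6 points down the table.

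**5. Visit 5 or the average?** The answer turns on the assumed course. The baseline-adjusted average matched or beat Visit 5 in 25 of the 32 courses, but in only 25 of the 96. In the table it wins at a half-time of 28 days. If the benefit exists at Visit 5 only, the average has 11-18% power where Visit 5 has 80%. In that same case a six-degree-of-freedom joint test has 61-77% under compound symmetry with correlation 0.3-0.7, but 82-90% under AR(1) correlation 0.7-0.9.

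**6. Type I error.** With equal recovery, rejection was 0.03-0.07 for all tests in the 96 courses (F reference). In the simulation of step 4 the joint Wald test ran at 7-9%. I attribute that to the test's small-sample behaviour, since the timing of the visits cannot produce it when recovery is equal.

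**The case against.** The strongest reply is that speed of recovery is already the primary endpoint. LEFS is listed in section 3 as difficulty with activities, so status at RTS and a month later is a legitimate secondary question, and a main contrast at about day 14-20 would largely measure the primary again. This stands. It is a reason to label the later values correctly and to leave the main contrast to the sponsor.

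A reader might infer that 9.4.3 prescribes a joint by-visit test that loses power, and that Visit 5 should therefore become the main contrast. The documents do not support this. They name no joint test, the one numerical clue (87) fits an average, and neither contrast wins across the assumed courses. Part of the apparent advantage of Visit 5 over a joint test of change is baseline adjustment, and part is the handling of early RTS.

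The baseline wording in 9.4.3 could also be meant as a covariate. If so, one phrase settles it.

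The early-RTS rule has its own weakness. It applies to different shares of each arm (1-24% of DSP children in the 96 courses, 11-76% in the simulation of step 4), and RTS is judged by therapists who know who is in Group C (4.2, 6.3). Applied without regard to the Clinic Check, it would also overwrite a real Visit 5 value in a child who relapsed and resumed treatment. Hence the restriction to confirmed RTS and the sensitivity analysis below.

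**Conclusion.** The point holds for efficiency and interpretation. For children who meet RTS, LEFS after Visit 5 describes status at and after RTS. On a plain reading, 9.4.3 uses change where adjustment for baseline would be more precise, and a by-visit analysis drops children with early confirmed RTS from Visit 5. Adjustment is worth a rise from 14-58% to 39-97% for the averaged contrast in the 32 courses. The early-RTS loss is up to about 1.1 points.

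All sizes rest on assumed recovery courses, SDs and visit spacing, because the documents give none. Type I error is not affected under equal recovery with RTS judged alike in all arms.

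The clinical stake is modest. In the 96 courses at 1.5-fold the differences are 2.4-4.4 points at Visit 5, 0.9-3.2 at RTS or Visit 12 and 0.2-3.2 thirty days later, all below the form's 9 points.

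Nor do the documents support reading a direction of bias into the FACES odds ratio. Its time coding and working correlation are simply unstated.

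**What to change.** In 9.4.3:

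- Keep the GEE. Enter baseline LEFS as a covariate, or constrain the baseline means to be equal. The second option gains precision only if the working correlation is not independence.
- Name the arm pairs: DSP vs placebo and DSP vs PT alone.
- For the Visit 5 time point, use the RTS-visit LEFS only for participants whose RTS was confirmed at the Clinic Check before Visit 5. If the check failed and treatment resumed, use the observed Visit 5 value.
- Report the baseline-adjusted Visit 5 difference beside the average over post-baseline times. The sponsor chooses the main contrast and fixes it before unblinding.
- Describe the RTS-visit and 30-day LEFS as status at and after RTS.
- Add a sensitivity analysis using observed Visit 5 values only.

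Two clarifications belong with this. State the FACES time coding and working correlation; no extra FACES reading is needed. Reconcile 4.1, 7.1 and 8.1 on when the 30- and 90-day contacts start for participants who do not meet RTS. The adverse-event window in 8.3.4 and the five-month duration (56 + 90 = 146 days) hint at Week 8, but no section says so for the contacts.

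The cost is wording and one added analysis, on data already collected. The downside is reliance on therapist-judged RTS at Visit 5, which the sensitivity analysis exposes.

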7 STUDY INTERVENTION DISCONTINUATION AND PARTICIPANT DISCONTINUATION/WITHDRAWAL

7.1 DISCONTINUATION OF STUDY INTERVENTION

Iontophoresis will be discontinued at the earlier of the following time points:

- The participant meets the RTS criteria
- The participant has completed 12 iontophoresis patch applications
- The participant has been receiving iontophoresis treatment for 8 weeks
- The participant develops any medical condition for which full participation in PT (including, but not limited to iontophoresis) would be contraindicated
- The participant meets an exclusion criterion (either newly developed or not previously recognized) that precludes further study participation

Discontinuation from iontophoresis does not mean discontinuation from the study, and remaining study procedures should be completed as indicated by the study protocol. If a clinically significant finding is identified (including, but not limited to changes from baseline) after enrollment, the investigator or qualified designee will determine if any change in participant management is needed. Any new clinically relevant finding will be reported as an adverse event (AE).

The data to be collected at the time of study intervention discontinuation will include the following:

- Brief physical exam of the affected knee
- Adverse event review and evaluation
- Concomitant medication review
- FACES Pain Scale
- RTS Checklist
- 30-day Phone Follow-up
- 90-day Survey Follow-up
- LEFS

Subjects who experience a relapse of pain after the Clinic Check Visit and prior to the 90-day Follow Up will not receive additional iontophoresis treatment as part of the study plan. Subjects who fall into this category will be treated with standard of care treatment as determined by the Treating Therapist or referring physician.

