- FACES Pain Scale (see Appendix 12.2) a patient reported paper-based questionnaire that asks the patient to choose the face that best represents the pain they are experiencing in their knee. Assessed at the end of each Study Treatment Visit and again at the end of the Clinic Check Visit.
- RTS Criteria Checklist (see Appendix 12.3) a paper-based checklist completed by the Treating
 Therapist to determine whether or not the participant is ready to safely return to sport. The
 checklist was created to include the basic movements typically required for sports activities,
 though these activities are also applicable for return to PE participation and free play, making it
 appropriate for all patients, even those not involved in organized sports. These movements
 include squatting, running, bilateral and unilateral jumping, back pedaling, and quick direction
 changes. The checklist includes qualifying criteria for proper mechanics and requires that all
 activities be pain-free. The checklist was created to assess readiness for sports participation
 without actually requiring that the patient return to sport participation to meet criteria, as not
 all patients participate in organized sports or are in-season year round. The items assessed as
 part of this checklist are all part of normal standard of care for physical therapy. Assessed at
 each Study Treatment Visit and again at the Clinic Check Visit.
- Godin Leisure-Time Exercise Questionnaire (see Appendix 12.4) a paper-based subject self-reporting questionnaire comprised of four (4) items that address the amount of time an individual engages in mild, moderate, and strenuous leisure time physical activity of at least 15 minutes in duration during a typical week. Assessed at Study Treatment Visit 1 and at the 30-day phone follow-up (see Appendix 12.5 30-Day Phone Follow Up) and 90-Day Follow-Up (see appendix 12.6 90-Day Follow-Up Electronic Survey).
- Study Treatment:
 - Iontophoresis (Groups A and B only) ~ 3 minutes in clinic and 2 hours at home The iontophoresis patch will be applied by a trained therapist in blinded fashion for all participants assigned to groups A and B (see section 6.1.2 Dosing and Administration). Performed at Study Treatment Visits 1 12 (Maximum of 12 treatments, maximum of 8 weeks since first Study Treatment Visit, or when RTS criteria are met and confirmed at the Clinic Visit Check, whichever is sooner).

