 - For subjects assigned to Group "C" (PT only Group), Study Treatment Visits 1 12 (maximum of 8 weeks since first Study Treatment Visit, or when RTS criteria is met) will

include only their standard PT Treatment Visits: Study Treatment 1 = Standard PT Treatment 1, Study Treatment 2 = Standard PT Treatment 2....).

Note: Participants who initially meet RTS Criteria but fail to meet the RTS criteria when they return for their Clinic Visit Check will continue with their assigned study treatment until the sooner of: they once again achieve RTS criteria, they have received 12 study treatments, or they have received study treatment for eight (8) weeks.

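### Visit 5 LEFS is missing by outcome for children whose early return to sport is confirmed, and the GEE does not say how that occasion is handled

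*Combined protocol and SAP*

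**What the plan says.** On LEFS timing, section 8.1 reads: "Assessed at Study Treatment Visits 1, 5, 12/RTS Criteria Met Visit, and 30-day Follow Up". The Schedule of Activities (1.3) marks LEFS at Visit 1, Visit 5, the last treatment visit, the early stop visit and the 30-day call, but not at the Clinic Check. The last treatment visit is event-driven; its column is headed "12 or Week 8, or when Return To Sport Criteria Met".

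Section 8.1 has the RTS checklist completed at each study treatment visit, so RTS can be met before Visit 5. For the two iontophoresis groups, study treatment runs to 12 treatments, 8 weeks, "or when RTS criteria are met and confirmed at the Clinic Visit Check, whichever is sooner". For PT alone the limit is "maximum of 8 weeks since first Study Treatment Visit, or when RTS criteria is met". A note then adds an exception, under which the allocated treatment resumes: "Participants who initially meet RTS Criteria but fail to meet the RTS criteria when they return for their Clinic Visit Check will continue with their".

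Section 7.1 includes LEFS in a list introduced by "The data to be collected at the time of study intervention discontinuation will include the following". Section 4.1 fixes the anchor of the later call: "All participants will receive a phone follow-up call 30 days after they meet RTS criteria".

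The analysis is in 9.4.3: a GEE with baseline records "will be used to check for changes in LEFS, FACES pain scale, and Godin Leisure-Time Exercise between treatment groups over time". It states no time coding, working correlation or rule for absent records. The check on non-informative censoring in 9.4.2 concerns the primary endpoint only.

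**The concern.** Visit 5 is the one post-baseline LEFS whose timing does not depend on recovery or on the end of treatment. A child with confirmed early RTS has no record there, and the reason is the outcome that the treatment is meant to hasten. The missing share would be larger in whichever arm recovers faster.

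The other occasions do not fill the gap. At the RTS-met visit every recovered child has just passed a pain-free functional checklist, at a date that varies by child, so the arms look alike among recoverers however fast they got there. The 30-day score is also counted from RTS.

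An unweighted GEE is in general valid only when records are missing completely at random, given the covariates in the model. If visit enters as a factor, the Visit 5 contrast is made among children not yet recovered. At stake is the LEFS comparison at that occasion, for a named secondary endpoint.

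**Working it through.** **Plan's own figures.** Section 9.2 gives 126 participants for f = 0.28, three groups, 80% power and alpha 0.05. A one-way F test with noncentrality N·f² and N − 3 denominator degrees of freedom gives a minimum N of 126 (power 80.02%), so it reproduces. The 87 for patient reported outcomes cannot be reproduced, because no effect size, SD or correlation is given. No figure in the documents describes how many children reach RTS before Visit 5.

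**Which LEFS records exist, by RTS history**

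| Child | Visit 5 LEFS | Other post-baseline LEFS |
|---|---|---|
| RTS met at Visits 2–4, Clinic Check passed | none | RTS-met visit, 30-day call |
| RTS met at Visits 2–4, Clinic Check failed | possible, since study treatment resumes | later last-visit score |
| RTS not met before Visit 5 | yes | last-visit score; 30-day call if RTS is met |

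**Size under assumed recovery times.** Every input here is an assumption, apart from the visit pace and arm size.
- Two visits a week (the maximum in 6.1.1) puts Visit 4 at 3 × 3.5 = 10.5 days and Visit 5 at 4 × 3.5 = 14 days.
- Time to RTS is gamma with shape 1.5 to 3 and control median 21 to 42 days. DSP shortens it by 25% to 35%.
- LEFS rises linearly from baseline (mean 52, SD 10) to about 76 at recovery, with measurement SD 3.
- RTS by day 10.5 removes the Visit 5 score.

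Worked case: shape 3, control median 28 days, 35% shortening. The scale is 28/2.674 = 10.47 for control and 0.65 × 10.47 = 6.81 for DSP. For shape 3, P(T ≤ t) = 1 − e^(−x)(1 + x + x²/2) with x = t/scale.
- Control: x = 10.5/10.47 = 1.003, so the missing share is 1 − 0.3669 × 2.506 = 0.081.
- DSP: x = 10.5/6.81 = 1.543, so the missing share is 1 − 0.2138 × 3.733 = 0.202.
- All three arms: (2 × 0.081 + 0.202)/3 = 0.121.

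Across the grid (simulation, 400,000 children per arm), 3% to 24% of control children, 6% to 39% of DSP children and 4% to 29% of all children lack a Visit 5 score. The difference in LEFS change among those observed is about 80% to 88% of the full-sample difference.

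**Does the direction hold under other assumptions?** A second model works in SD units with a true mean difference of 0.50 SD. Latent recovery speed is normal, and RTS correlates with it at 0.3, 0.6 or 0.9. The control share with RTS by Visit 4 is 5% to 40%.

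Closed-form check for a uniform benefit, 20% early RTS in control and correlation 0.6. The cut-off is c = 0.8416, and the DSP arm's RTS score is shifted by 0.6 × 0.5 = 0.3.
- Control mean among those observed: −0.6 × 0.2800/0.8000 = −0.210.
- DSP mean among those observed: 0.5 − 0.6 × 0.3445/0.7060 = 0.207.
- Difference: 0.207 + 0.210 = 0.417 SD. The simulation gives 0.42 SD (84%).

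| Who benefits | Visit 5 difference among those observed (truth 0.50 SD) |
|---|---|
| All children equally, RTS also faster | 0.25 to 0.49 SD (50% to 98%) |
| Fast recoverers only | 0.44 down to −0.28 SD |
| Slow recoverers only | 0.52 to 0.65 SD (103% to 129%) |
| LEFS improves but RTS is unaffected (20% early, correlation 0.6) | 0.50 SD |
| RTS unrelated to LEFS (20% early) | 0.50 SD |

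If 20% of early RTS children fail the Clinic Check, the closed-form example moves from 0.42 to 0.45 SD (89%).

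**The case against.** The strongest reply is that 9.4.3 names no Visit 5 contrast. It plans one GEE over time, and early recoverers stay in it with baseline, RTS-met and 30-day scores. The simulations describe a Visit 5 comparison, not that GEE, and how far its estimate moves depends on time coding that is not stated. This stands, and it limits the point to one occasion. It does not remove it: a GEE by group and visit would estimate that contrast, and any other coding leaves the result resting on an unstated choice.

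The first model also ties LEFS closely to recovery time, which builds in attenuation. Early RTS may be uncommon, since the checklist in 12.3 requires jumps, a triple hop and a modified T-test, all pain-free. At a 42-day median only 4% to 13% of children are missing. Both remarks are fair.

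Four stronger readings are tempting, and the documents do not support them.
- A reader might infer that no child who meets RTS at Visits 2 to 4 can have a Visit 5 score. The note in 8.1 returns those who fail the Clinic Check to study treatment.
- A reader might infer that any DSP benefit shrinks. The second table shows no change in two cases and inflation in another.
- A reader might infer that too few children remain. Even at 29% missing, 126 × 0.71 is about 89, against the 87 that 9.2 requires.
- A reader might infer that the trial's test of faster recovery is lost. Days to RTS is the primary endpoint, and it counts early recoverers directly.

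**Conclusion.** The point holds in limited form. The gap follows from the stated schedule: confirmed RTS at Visits 2 to 4 leaves no Visit 5 LEFS, that absence is caused by the outcome, and 9.4.3 does not address it. If DSP speeds RTS broadly and LEFS tracks RTS, the Visit 5 difference is biased toward zero, to about 80% to 88% of its full value under the assumed recovery times, and to 50% to 98% when the link between LEFS and RTS is varied. These figures are illustrative, because the documents give no RTS distribution, LEFS SD or correlation between the two. Neither the size nor the direction can be settled from the documents, which is a reason to specify the handling in advance.

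**What to change.** In 1.3 and 8.1, collect LEFS from every child at the time Visit 5 would fall, counted from Study Treatment Visit 1 and whatever the RTS status, with a stated target day and window. Use a standard PT visit or the Clinic Check if one falls then. Otherwise take it by phone, as is already done at 30 days.

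In 9.4.3, code this occasion by time since Visit 1. If the score is still absent for a child with confirmed RTS, use the RTS-visit LEFS for that occasion, and add a sensitivity analysis without it. State how that score is then counted, so that one measurement does not silently enter the model as two. For children already past that time, only this fallback is available.

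The cost is one extra self-completed form for early recoverers and a few sentences of text. Where the fallback is used, it assumes that function holds for the few days between RTS and the time Visit 5 would have fallen. That is why a real score is preferable to carry-forward alone. Treatment and visit rules do not change.
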